8.1 Assessment of AEs by direct question to subject and evaluation of subject

Safety evaluations for this study include an interview of the subjects at each visit to obtain information about any medical occurrence that meets the definition of an AE. Each subject should be questioned about AEs at each study visit following the screening visit. Information on AEs can also be obtained from signs and symptoms detected during each examination by the Investigator or designee, which should include visual inspection of the treatment area.

AEs must be documented in the source document and eCRF without regard for cause or relation to investigational product. If in the process of the interview, additional information regarding medical history or pre-planned medical or surgical procedures is revealed, it must be documented in the source document(s) and eCRF.

It is the responsibility of the Treating Investigator to determine severity of the AE and relatedness of the event to the study product.

A series of horizontal black bars of varying lengths and positions on a white background, suggesting redacted text. The bars are irregular in length and position, creating a stepped effect across the page. There are small black squares at the far left and right edges of the bars.

8.6 Laboratory Assessments

Pregnancy Test: For all women of childbearing potential, a urine pregnancy test will be performed at screening, all injection visits (prior to treatment) and at study exit. The test result will be documented.

8.7 Adverse events

8.7.1 Definition of an adverse event

An AE is any untoward medical occurrence, unintended disease or injury, or untoward clinical signs (including abnormal laboratory findings) in subjects, users or other persons¹, whether or not related to the study product.

This definition includes:

- a) events related to the investigational product or the reference product
- b) events related to the procedures involved

8.7.2 Definition of a serious adverse event

A serious adverse event (SAE) is an AE that:

- a) led to death,
- b) led to serious deterioration in the health of the subject, that either resulted in
 1. a life-threatening² illness or injury, or
 2. a permanent impairment of a body structure or body function, or
 3. in-patient or prolonged hospitalization³, or
 4. medical or surgical intervention to prevent life-threatening illness or injury or permanent impairment to a body structure or a body function,
- c) led to fetal distress, fetal death, or a congenital abnormality or birth defect

An AE does not need to be recorded as a SAE if it only represents a relapse or an expected change or progression of the condition that was the cause of the treatment, without the development of new symptoms and signs.

In cases of doubt, whether an AE fulfils a serious criterion or not, there should be a predisposition to report as a SAE rather than not report as such

8.7.3 Recording instructions

Each subject with an AE occurring after signing of the informed consent form through study exit should be fully recorded in the source document for further transcription to the eCRF. Each subject should be questioned about AEs at each study visit following the screening visit. The question asked should be: "Since your last clinical visit have you had any health problems?" Information on AEs can also be obtained from signs and symptoms detected during each examination.

¹For users or other persons, this definition is restricted to events related to the investigational product.

²The term "life-threatening" in the definition of "serious" refers to an event in which the patient was at risk of death at the time of the event; it does not refer to an event which hypothetically might have caused death if it were more severe. (Source: ICH-E2A clinical safety data management: definitions and standards for expedited reporting).

³Planned hospitalization for a pre-existing condition, or a procedure required by the CIP, without serious deterioration in health, is not considered a SAE. (Source: ISO14155:2011).

When an AE is related to a device deficiency including technical device malfunction, the AE should be recorded in the AE eCRF and technical complaint should be reported separately on the study complaint form.

Investigators, or other study site personnel, shall record all AEs in the eCRF, including:

- a) Event term (recorded in standard medical terminology and avoiding abbreviations)
- b) Description of event and affected area
- c) Start date (first day with symptoms)
- d) Stop date (last day with symptoms)
- e) Intensity (mild, moderate, or severe according to definition in Section [8.5.3.1](#))
- f) Seriousness (serious or not serious, according to definition in Section [8.5.3.2](#))
- g) Causal relationship to study product or study product injection procedure (yes or no)
- h) Action taken (none, medication treatment, non-medication treatment, or other procedures/tests, subject withdrawn)
- i) Outcome of the AE (ongoing, recovered, recovered with sequelae, death, chronic/stable, not recovered at the end of the study)

The pre-defined, expected post-treatment events shall be assessed separately. These events shall be collected by subjects in a diary used daily for 30 days after the treatment.

8.7.3.1 Intensity

Intensity will be recorded for each reported AE. The following definitions of intensity are to be used:

Mild: Awareness of symptoms or signs, but easily tolerated (acceptable)

Moderate: Enough discomfort to interfere with usual activity (disturbing)

Severe: Incapacity to work or to do usual activity (unacceptable)

If the intensity changes within one day, the maximum intensity of the AE during that day shall be recorded.

8.7.3.2 Causal relationship and seriousness

Each AE, serious as well as non-serious, shall be assessed by the Investigator for causal relationship with the study product and its use (the injection procedure) and for seriousness (Yes or No) of the event.

A two-point scale (Yes or No response) shall be used for the causality assessments. The Investigators shall be asked to indicate a response to each of the following questions in the eCRF:

- “Do you consider that there is a reasonable possibility that the event may have been caused by the study product?”, and
- “Do you consider that there is a reasonable possibility that the event may have been caused by the device injection procedure?”

If any of these questions is answered ‘Yes’, the AE is considered related.

Each AE will also be assessed for causal relationship and seriousness by the Sponsor, in order to fulfil regulatory requirements.

8.7.4 Reporting of adverse events

Adverse event reporting on each subject shall start at screening visit after the signature of the ICF. The reporting shall continue during each follow-up visit (including telephone contacts and extra visits between planned visits) until the last scheduled visit in the study.

All AEs, non-serious as well as serious, are to be reported as an AE in the eCRF.

Follow-up information and data missing in the initial SAE reporting shall be gathered as soon as possible and reported immediately but not later than 24 hours of awareness of the new data. Complete and adequate information on each SAE is required. All attempts to obtain this information, including dates for follow-up activities, must be documented by the Investigator or designated study staff.

Supporting documentation to be provided with the SAE report:

- Concomitant medication form
- Concomitant procedure/treatment form
- AE form
- Medical history form
- Any other relevant supporting documentation (e.g. hospital notes, death certificate, autopsy reports etc.)

The SAE form must be signed and dated by the Investigator. If the initial 24-hour SAE report does not contain full information or if it is made without using the SAE form the fully completed and signed SAE form shall be e-mailed to the Sponsor. A copy of the fully completed SAE form shall be kept at the site.

In addition, the Investigator shall report SAEs to the responsible IRB without undue delay, if applicable according to national regulations. The Investigator is responsible for checking what reporting procedures are applicable for his/her IRB regarding SAEs and final report of the outcome of the study and to comply with such reporting procedures during the study period. For non-urgent complementary information not possible to send by e-mail or fax, please use surface mail.

8.7.7 Pregnancy

Pregnancy itself is not regarded as an AE.

If there is a pregnancy after the subject has been treated, the subject must continue to be followed within the study and the outcome of pregnancy must be reported even if the delivery occurs after study completion.

A pregnancy confirmed during the study period after treatment must be reported by the Investigator on a pregnancy report form immediately upon acknowledgement and submitted to the Sponsor according to contact details specified in Section [8.7.5](#). The report can be prospective or retrospective. Follow-up shall be conducted to obtain outcome information on all prospective reports.

Cases that led to fetal distress, fetal death or a congenital abnormality or birth defect are to be regarded as SAEs and shall be reported on the exposure *in utero* report form to the Sponsor immediately but no later than 24 hours after the Investigators awareness. These events shall be handled as SAEs during data processing. Other complications during the pregnancy that are related to the pregnant woman and fulfils any serious criteria, such as pre-eclampsia requiring hospitalization, shall be reported and handled as SAEs. Elective abortions without complications shall not be reported as AEs.

8.8 Device deficiencies

8.8.1 Definition of a device deficiency

A device deficiency is defined as an inadequacy of a medical device with respect to its identity, quality, durability, reliability, safety¹, or performance.

Note: Device deficiencies include malfunctions, use errors, and inadequate labelling.

8.8.2 Recording instructions

When a device deficiency is discovered, Part A of the clinical study complaint form shall be completed by the Investigator or qualified designee. The type of complaint shall be described and injury to the subject or user or unintended exposure to study product shall be reported as applicable. If an injury has occurred, an AE or an SAE form shall be completed as applicable (refer to Section [8.7](#)). If no SAE was experienced as a result of the device deficiency the Investigator shall assess whether or not the device deficiency could have led to an SAE if:

- Suitable action had not been taken,
- Intervention had not been made or,
- Circumstances had been less fortunate

In Part B of the clinical study complaint form the Sponsor will make the same assessment.

8.8.3 Reporting of device deficiencies

A device deficiency that led to a SAE and any device deficiency that could have led to a SAE shall be reported within 24 hours after the Investigator's awareness in accordance to Section [8.7.5](#).

In order to fulfil regulatory reporting requirements, all deficiencies with the study product must be assessed by both the Investigator and the Sponsor to determine if it could have led to a SAE.

If a SAE has resulted from a device deficiency or if either the Investigator or the Sponsor assesses that the device deficiency could have led to a SAE the Sponsor is responsible for reporting the device deficiency to RA and the PI is responsible for reporting it to the IRB.

The deficient study product shall be kept by the study site until the Sponsor has confirmed whether the product shall be returned to Sponsor for further study or if it can be destroyed at the study site.

9. Data Handling and Management

9.1 Data management

Data management based on GCP refers to the activities defined to achieve safe routines to enter clinical data information into a database, efficiently and avoiding errors. The data management routine includes procedures for handling eCRFs, database set-up and

¹Inadequacy of device safety refers to properties of the device which could have or have led to an AE.

management, data entry and verification, data validation, and documentation of the performed activities including information of discrepancies in the process. The data management process will be described in detail in the data management plan (DMP).

The database, the data entry screens and program will be designed in accordance with the CIP and the eCRF. Data validation will be performed by computerized logical checks and manual review. Drugs and events will be coded in accordance with World Health Organization (WHO) Drug and medical dictionary for regulatory activities (MedDRA) dictionaries as specified in the DMP. SAEs in the clinical database will be reconciled against the data in the safety database.

When all efforts have been made to ensure that the data recorded in the eCRFs and entered in the database is as correct and complete as possible, the clinical database will be locked. Study data will be transferred to SAS datasets which thereafter will be write-protected. Statistical analyses will be generated in SAS using data from the locked datasets.

9.2 Electronic case report forms

A 21 Code of Federal Regulations Part 11-compliant electronic data capture application will be used to collect, modify, maintain, archive, retrieve, and transmit study data. An eCRF is required and shall be completed electronically for each screen failure as well as enrolled subjects.

The eCRF includes password protection and internal quality checks, such as automatic range checks, to identify data that appear inconsistent, incomplete, or inaccurate. Study data shall be entered directly from the source documents, which are to be defined at each site before inclusion of the first subject.

Authorized study site personnel designated by the Investigator shall complete data collection. Appropriate training and security measures shall be completed with all authorized investigation site personnel prior to the study being initiated and any data being entered into the system for any subject.

The study data is the sole property of the Sponsor and shall not be made available in any form to third parties, except for authorized representatives of appropriate RA, without written permission from the Sponsor. At the end of the study, electronic data are kept at the Sponsor and a copy (provided by the vendor) at the study site as part of the Investigator file.

Any delegation of collection of data shall be specified in a signature and delegation log.

9.2.1 Data entry

All data shall be entered in English. The eCRFs should always reflect the latest observations on the subjects participating in the study. Therefore, the eCRFs shall be completed as soon as possible during or after the subject's visit. The subject's identity must always remain confidential, i.e. the name and address of the subjects must not be registered in the eCRFs or in the database. The Investigator must verify that all data entries in the eCRFs are accurate and correct. If some assessments are not done, or if certain information is not available, not applicable or unknown, the Investigator shall indicate this in the eCRF. The Investigator shall electronically sign off the study data. By signing, the Investigator takes responsibility for the accuracy, completeness, and legibility of the data reported to the Sponsor in the eCRF.

9.2.2 The query process

The monitor shall review the eCRFs and evaluate them for completeness and consistency. Each eCRF shall be compared with the respective source documents to ensure that there are no discrepancies between critical data. All entries, corrections, and alterations shall be made by the PI or his/her authorized designee. The monitor cannot enter data in the eCRFs. Once study data have been submitted to the central server via the eCRF, corrections to the data fields will be audit trailed, meaning that the reason for change, the name of the person who made the change, together with time and date will be logged. Roles and rights of the site personnel responsible for entering study data into the eCRF shall be determined in advance. If discrepant data is detected during review of the data, either by the Sponsor or its representatives, the responsible data manager or monitor shall raise a query in the electronic data capture application. The query shall state the question or data to be changed and shall be resolved in the system by the PI or his/her authorized designee. The appropriate study site personnel shall answer the queries in the eCRF. This will be audit trailed by the electronic data capture application meaning that the name of study site personnel, time, and date is logged.

9.2.3 User identification

eCRF records will be automatically appended with the identification of the creator, by means of their unique User ID. Specified records shall be electronically signed by the Investigator to document his/her review of the data and acknowledgement that the data are accurate. This will be facilitated by means of the Investigator's unique User ID and password; date and time stamps will be added automatically at time of electronic signature. If an entry in an eCRF requires change, the correction shall be made in accordance with the relevant software procedures.

9.2.4 Audit trail

All changes will be fully recorded in a protected audit trail and a reason for the change shall be stated. Once all data have been entered, verified, and validated, the database will be locked.

9.3 Source documents

Source documents are all documents used by the Investigator or hospital that relate to the subject's medical history, that verifies the existence of the subject, the inclusion and exclusion criteria, and all records covering the subject's participation in the study. They include laboratory notes, memoranda, material dispensing records, subject files, etc.

The Investigator is responsible for maintaining source documents. These shall be made available for inspection by the monitor at each monitoring visit. The Investigator must submit a completed eCRF for each subject for whom signed informed consent has been collected. All supportive documentation submitted with the eCRF, such as laboratory or hospital records, shall be clearly identified with the CTN and subject number. Any personal information, including name, shall be removed or rendered illegible to preserve individual confidentiality.

9.4 Record keeping and access to source data

The Investigator/Institution shall permit study-related monitoring, audits, IRB review, and RA inspections and shall provide direct access to the source data/medical record including

the identity of all participating subjects (sufficient information to link records, i.e. eCRF, medical records, original signed informed consent forms and detailed records of study product accountability). The records shall be retained by the Investigator as required by local legislation and international guidelines. Any transfer of responsibility for storage of the records shall be documented and the Sponsor shall be informed in writing.

The Sponsor shall verify that each subject has consented in writing to direct access to the original medical record/source data (by the use of written subject information and signed informed consent). The data recorded in the eCRFs will be checked for consistency with the source documents/medical record by the monitor during monitoring (source data verification; SDV). In order to be able to perform SDV, information about each subject's participation in the study has to be detailed in the medical record.

9.5 Document and data retention

All records pertaining to the conduct of the study, including signed eCRFs, informed consent forms, study product accountability records, source documents, and other study documentation must be retained for as long as is specified in the CTA. Measures shall be taken to prevent accidental or premature destruction of these documents (e.g. protection against damage and unauthorized access, preferably by storage in a fire-proof cabinet).

It is the Investigator's responsibility to inform the Sponsor in writing if the Investigator file is moved or if the responsibility for the documents is transferred to someone else.

10. Statistical Methods

10.1 General

A large rectangular area of the page is completely blacked out, indicating that the content has been redacted. There are a few small white rectangular gaps in the black area, likely where text was partially visible before being redacted.

10.3 Demographics, baseline assessments, and subject characteristics

Demographic endpoints, baseline assessments, and subject characteristics will be presented based on the ITT analysis set using descriptive statistics by treatment, as appropriate.

10.4 Efficacy analysis

[REDACTED]

[REDACTED]

[REDACTED]

[REDACTED]

[REDACTED]

[REDACTED]

[REDACTED]

10.5 Safety analysis

Number and percentage of subjects reporting each pre-defined, expected, post-treatment symptoms, as collected in the 30 day diary, will be presented in total and by maximum severity. Number of days with the event will also be summarized using mean, SD, min, max, and median.

[REDACTED]

[REDACTED]

[REDACTED]

[REDACTED]

10.6 Handling of missing data

Number of missing values will be summarized and reported as appropriate. Missing data for the primary analysis will be handled using the hot deck imputation method.

[REDACTED]

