## 2 Statistical Methods

### 2.1 General methods

All statistical analyses, including summary tables and data listings, will be performed using the SAS® system (Version 9.3 or higher). Confidence intervals (CIs) will be two-tailed and constructed at a confidence level of 95%. P values will be two-sided and performed at a significance level of 5%.

All study data including observed and derived variables (e.g., change from baseline, response status) used in the summaries of analyses will be presented in by-subject listings. In general, efficacy, safety, demography, subject characteristics, and treatment related variables will be presented using descriptive statistics. For categorical parameters, the number and percentage of subjects in each category will be presented. The denominator for percentage will be based on the number of observations at that time point (i.e. observed cases). For continuous parameters, descriptive statistics will include number of observations, mean, standard deviation (SD), median, and range. Graphs will be used as appropriate.

Any change made to the finalized statistical analysis plan (SAP) after database lock will be documented in the Clinical Study Report (CSR).

For the primary analysis, non-inferiority will only be demonstrated if the CI is entirely below 0.5 for both co-primary endpoints in both the ITT and PP populations. Similarly, superiority will only be demonstrated if the lower confidence limit is entirely below 0 for both co-primary endpoints in both the ITT and PP populations. Therefore no multiplicity adjustment for Type I error is required.

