### 2.4.2 Handling of missing data

Number of missing values will be summarized and reported as appropriate.

[REDACTED]

Impact of missing data on the primary analysis for Week 8 endpoint will be evaluated by performing sensitivity analysis based on the observed cases in the ITT population.

All other endpoints will be evaluated based on the observed cases in ITT, i.e. no imputations will be done.

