### 2.4.3 Primary efficacy analysis

Non-inferiority will be established if the CI is entirely below 0.5 for both co-primary endpoints in both the ITT and PP populations. Superiority will be declared if the CI is entirely below 0 for both co-primary endpoints in both the ITT and PP populations. This decision criteria is consistent with a gate-keeping strategy (testing for superiority following the test for non-inferiority) to maintain the overall type I error rate at 5%.

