## 2.7 Determination of Sample Size

[REDACTED]. Accounting for approximately 15% drop-outs and non-evaluable subjects due to protocol deviations at week 8, a total of approximately 280 subjects will be randomized in the study. It is expected that the number of randomized subjects will be similar across the study sites.

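### If the hot deck for missing Week 8 scores is a single fill analysed as observed data, the ITT 95% CI that gates both claims is too narrow; the readable plan does not say how its variance is obtained

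*Protocol*

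**What the plan says.** Protocol 10.6 gives the imputation rule in one sentence: "Missing data for the primary analysis will be handled using the hot deck imputation method". A redacted block follows it directly.

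SAP 2.4.2 has a redacted block where the primary rule would stand. The readable remainder says that the impact of missing Week 8 data will be judged by "performing sensitivity analysis based on the observed cases in the ITT population". It adds: "All other endpoints will be evaluated based on the observed cases in ITT, i.e. no imputations will be done". Imputation is therefore confined to the primary analysis.

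On the interval, SAP 2.1 says: "Confidence intervals (CIs) will be two-tailed and constructed at a confidence level of 95" per cent. SAP 2.4.3 then uses it as a decision rule: "Non-inferiority will be established if the CI is entirely below 0.5 for both co-primary endpoints in both the ITT and PP populations". The rule for a superiority claim has the same form, with 0 as the bound in place of 0.5.

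The same section describes the testing order as a way "to maintain the overall type I error rate at 5" per cent. SAP 2.2 limits PP to ITT subjects who complete the Week 8 visit without a deviation of substantial impact, so PP in effect contains no imputed Week 8 scores.

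On the amount of missing data, SAP 2.7 says: "Accounting for approximately 15% drop-outs and non-evaluable subjects due to protocol deviations at week 8". SAP 1.1.2 aims for 234 evaluable subjects from about 280 randomised.

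**The concern.** A hot deck fills each missing score with the score of an observed subject. If this is done once and the completed file is analysed as 187 and 93 real observations, two things go wrong. Copied scores are counted as new information, and the chance choice of donor adds variation that the standard error ignores. The standard error is too small even when the data are missing completely at random.

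The ITT interval is one of the two gates for each claim, and the study report goes into a marketing submission. If the variance is not corrected, an interval labelled 95% has lower coverage and the ITT gate is easier to pass than intended. The planned sensitivity comparison is distorted too: the observed-case interval would look less precise than the primary one although both hold the same real data.

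**Working it through.** **Inputs from the documents.** 187 and 93 subjects (Protocol 4.1, SAP 1.1.1); 234 evaluable of about 280 (SAP 1.1.2); an allowance of about 15% (SAP 2.7); two-sided 95% CI, so 2.5% in the tail facing the margin (SAP 2.1).

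**The plan's own figure.** 234 / (1 - 0.15) = 275.3, rounded up to 276, against about 280 stated. This agrees to within rounding. The 234 itself cannot be rebuilt, because its inputs are redacted.

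**Assumptions.** A single hot deck; filled data analysed as observed; scores missing completely at random; donors drawn at random within arm; an unadjusted two-sample t interval (the primary model is not readable); the same missing fraction d in both arms. The documents give no separate figure for missing scores, so d runs from 2% to 15%. The top of that range is an upper bound: subjects excluded for protocol deviations may still have a Week 8 score.

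**Variance.** With r scores observed of n in an arm, and d = 1 - r/n:

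- true variance of the completed mean ≈ σ²/r + σ²(n - r)/n²
- variance reported if all n count as observed ≈ σ²/n
- ratio = n/r + (n - r)/n = 1/(1 - d) + d

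At d = 10%, for example, 1/0.90 + 0.10 = 1.2111, and its square root is 1.10. The true standard error is 1.10 times the reported one.

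**Coverage and width.** With s the square root of that ratio, coverage is 2Φ(1.96/s) - 1 and error in one tail is 1 - Φ(1.96/s). The observed-case standard error is proportional to 1/√r, so the reported ITT interval is √(1 - d) times the observed-case width.

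| d | Variance ratio | SE ratio s | Coverage | One-tail error | Width relative to observed cases |
|---|---|---|---|---|---|
| 2% | 1.0404 | 1.02 | 94.5% | 2.7% | 0.990 |
| 5% | 1.1026 | 1.05 | 93.8% | 3.1% | 0.975 |
| 10% | 1.2111 | 1.10 | 92.5% | 3.75% | 0.949 |
| 15% | 1.3265 | 1.15 | 91.1% | 4.4% | 0.922 |

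**Simulation.** 40,000 simulated trials at 187 and 93, with normal scores, gave single hot deck coverage of 94.5%, 93.9%, 92.5% and 91.1% at d = 2, 5, 10 and 15%, in line with the table.

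**Joint ITT-and-PP rule.** The joint false-claim rate cannot exceed the PP rate alone. With PP taken as the Week 8 completers, the simulated joint rate for one lip was 2.4%, 2.2%, 2.1% and 2.2% at the same four values of d. Requiring both lips can only lower it.

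**Alternative.** A multiple hot deck by approximate Bayesian bootstrap within arm, with 20 imputations and Rubin's rules, was simulated 6,000 times at each d. Coverage was 95.0-95.4%, and the interval was within about 0.1% of the observed-case width.

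**The case against.** The strongest objection is that the decisive text is hidden. Hot deck is a family of methods that includes multiple hot deck. Redacted blocks follow the sentence in Protocol 10.6, stand in SAP 2.4.2 and fill Protocol 10.4, and the readable part of SAP 2.4.3 starts at the decision rule with no model. Text that is redacted is not missing from the plan. This stands. A reader might infer that the hot deck is single and that the ITT interval is therefore too narrow as a matter of fact; the documents do not show that.

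A second objection is that the claims are protected. A reader might infer a breach of the stated 5% type I error rate. The documents do not support this, because PP must pass as well and under the assumptions above it caps the joint error. The cap need not hold if missingness depends on outcome, but that is a matter of bias, not of interval width.

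Third, the effect is small if few scores are missing: coverage is 94.5% at 2%. It would also be wrong to treat all 280 - 234 = 46 non-evaluable subjects (16.4%) as having no score.

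Fourth, the planned observed-case analysis already gives an interval with about the right width when data are missing completely at random. That is true, but it is a sensitivity analysis. The decision rules apply to the primary ITT interval.

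**Conclusion.** The point holds as a conditional one. The plan names hot deck for an analysis whose ITT interval gates both claims, and nothing readable carries imputation uncertainty into that interval. If the hot deck is single and its values are analysed as observed, the nominal 95% ITT CI covers about 94%, 92.5-93% and 91% at 5, 10 and 15% missing, and is about 3%, 5% and 8% narrower than the observed-case CI.

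These sizes rest on the assumptions listed in the working. The variance ratio does not depend on the shape of the scores; the coverage figures rest on a normal approximation. The consequence is limited to the coverage of the reported ITT CI and the leniency of the ITT gate.

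**What to change.** First confirm what the redacted text says. If it already sets out a multiple hot deck with Rubin's rules, or another variance estimator that is valid after imputation, no change is needed.

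Otherwise specify in Protocol 10.6 and SAP 2.4.2:

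- a multiple hot deck by approximate Bayesian bootstrap within randomised arm, with at least 20 imputations;
- estimates and CIs combined by Rubin's rules;
- the 0.5 and 0 rules applied to the combined ITT CI;
- coarse donor classes, for example arm and baseline lip fullness score. If about 21 subjects are FST V-VI (an assumption based on the figure in Protocol 4.1), 2:1 allocation leaves about 21/3 = 7 controls in that stratum, too few to split further. The simulation drew donors within arm only; finer classes were not tested.

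The cost is SAP and protocol wording and a short program, with no new data or subjects. The downside is a slightly wider ITT CI. From the simulated width ratios, it would exceed the uncorrected single hot deck CI by about 3% at 5% missing (1/0.973), 5.5% at 10% (1/0.948) and 9% at 15% (1/0.919). That is close to the observed-case width, and the PP analysis, which uses Week 8 completers only, already works at about that width or wider.
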